7.2 Record Retention

All records relating to the conduct of the Study are to be kept in a locked and secure location and held by the Principal Investigator until notified by the Sponsor that the records may be destroyed. Essential documents should be retained until at least 2 years after the last approval of a marketing application in an ICH region and until there are no pending or contemplated marketing applications in an ICH region or at least 2 years have elapsed since the formal discontinuation of clinical development of the investigational product. These documents should be retained for a longer period, however, if required by the applicable regulatory requirements or by agreement with the Sponsor. The Sponsor will notify the Principal Investigator of the retention period required to satisfy appropriate regulations. If the Sponsor has not notified the Principle Investigator and 10 years has passed since the last subject was enrolled, all records may be destroyed.

The Principal Investigator will allow representatives of the Sponsor's monitoring team and of the appropriate regulatory authority to inspect all Study records, CRFs, and corresponding portions of the Study patients' office and/or hospital medical records at regular intervals throughout the Study and after the Study has completed if required. These inspections are for the purpose of verifying adherence to the protocol, the completeness and exactness of the data being entered in the report forms, and compliance with regulations.

8.0 Study Analyses

8.1 Statistical Analysis Plan

Stabilization Phase

Stabilization Phase is not blinded. The malignancy or benignity status of the patients will be available as described in Section 4.0 Study Design. Algorithm stabilization will be tested by the Sponsor against prior clinical results and across study patients. In addition, in this phase, the Sponsor and Statistician may evaluate the impact of demographic, geographic and anatomical factors on the stability of the risk stratification Algorithm. Certain inter and intra patient bioconductance factors may also be evaluated for impact on Algorithm stability.

The statistical approach to the risk stratification Algorithm stabilization will be to modify the Algorithm using Optimal Data Analysis (ODA) programmed in Stata™ version 11 statistical software that allows a large number of variables at a time while treating each measurement variable independently. This will be in contrast to traditional multivariable regression that treats variables as possibly correlated, but only allows for a small number of predictor variables at a time which will also be used to optimize the Algorithm. Variable selection, cut-point determination, decision nodes, and so on, will be based on variables that provide improved discrimination and validate successfully.

After stability of the risk stratification has been confirmed by the Sponsor, the Algorithm will be locked, and further changes will not be permitted.

Validation Phase

The locked risk stratification Algorithm will be applied to the patients participating in the Validation Phase in which the Sponsor's Statistician is blinded to the actual patient diagnosis.

With respect to determining the optimal sample size of the Validation Phase, it is assumed that the sensitivity of the ProLung test (probability of having had a high risk test among subjects who subsequently had a malignant biopsy) is 70% and that the specificity (probability of having had a low risk test among subjects who subsequently had a benign biopsy) is also 70%. It is further assumed that among the patient population studied in this Study, approximately 70% will have a malignant biopsy. Based on these assumptions, 88 subjects will provide 90% power to reject the primary null hypothesis. The primary analysis will only include subjects who have a biopsy within 60 days of their ProLung test and have a definitive biopsy result. Subjects who fail to have a biopsy or do not have a definitive biopsy result will be excluded. To account for as many as 12% of such subjects, 100 subjects will be enrolled into the Validation Phase. Furthermore, to maintain the Study's statistical power, enrollment will continue until there is both a minimum of 100 subjects and a minimum of 40 ProLung high risk and a minimum of 40 ProLung low risk subjects are enrolled.

The primary null hypothesis is that the relative risk of a malignant biopsy among subjects with a high risk ProLung test result to that of subjects with a low risk ProLung test result is 1.0, vs. the alternative hypothesis that the relative risk is different from 1.0. This hypothesis will be tested by a two-sided Fisher's Exact Test at the 5% level of significance. If the relative risk is found to be greater than 1.0

($p < 0.05$), it will be concluded that subjects with a high risk ProLung test result are prognostically at greater risk to have a malignant biopsy than subjects with a low risk ProLung Test result. The relative risk will also be presented with its approximate 95% confidence interval.

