2.0 Study Objectives

2.1 Objectives and Aims

The primary Study hypothesis is that the ProLung Test will demonstrate safety and efficacy in the risk stratification of patients with pulmonary lesions identified by CT that are suspicious for lung cancer. A statistically significant result will indicate that patients with a high ProLung Test result have a greater risk of developing lung cancer than patients with a low test result.

There are three Specific Aims of this study:

1. Optimize and confirm the stability of the ProLung Test risk-stratification algorithm in patients with a diagnosis.
2. Externally validate the efficacy of the ProLung Test risk-stratification algorithm by comparing the test result to the conclusive patient diagnosis.
3. Assess the safety and tolerability of the ProLung Test procedures.

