3.0 Study Design

This Study consists of two distinct phases, Stabilization and Validation. The Study will collect data from multiple sites (3 to 20), and each site may enroll patients and collect data for the Stabilization and Validation Phases with a minimum of three sites for the Validation Phase. In this multi-center Study, the patient's known diagnosis (of either a malignant or benign outcome) will be compared to the ProLung Test results. The patient's diagnosis is determined by tissue biopsy, surgical resection or by CT follow-up detecting significant nodule growth during a 1 year time frame. This Study follows the National Comprehensive Cancer Network definition for nodule growth. Nodule growth is defined as: 1) for nodules 15 mm or smaller: an increase in mean diameter of 2 mm or more in any nodule or in the solid portion of a part-solid nodule when compared with the baseline scan, or 2) for nodules 15 mm or more: an increase of 15% in mean diameter when compared with the baseline scan. Mean diameter is the mean of the longest diameter of the nodule and its perpendicular diameter^{xii}. If no significant growth is detected and the nodule is not definitively diagnosed by biopsy or surgical excision, the outcome will be considered benign unless indicated otherwise in the patient's medical record.

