4.3.1 Events Necessitating Premature Discontinuation

The occurrence of any one of the following events may necessitate premature discontinuation of a subject from the Study:

- Subject develops any of the exclusion criteria after enrollment.
- Subject is unwilling to continue in the Study.
- Subject does not comply with the Study Protocol.
- Subject being followed by CT for nodule growth who does not receive a follow-up CT by their 1-year enrollment anniversary or within 60 days after their 1-year enrollment anniversary.

- Principal Investigator decision.

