4.3.2 Events Eliminating Subjects from Primary Analyses

- Incomplete or lost medical records.
- Inconclusive biopsy result.
- Incomplete ProLung Test data.

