5.10 Follow-up Outcome Assessment

The outcomes of any ancillary diagnostic procedures conducted as part of normal clinical care will be collected for further analysis and the provided CRF page(s) will be completed as appropriate. The Study participant will sign a "Release of Medical Information" at the time of the consent process. All laboratory and radiological tests performed to further evaluate the abnormal chest CT will be obtained by the study team and kept as part of the participant's source document. This will include but are not limited to results of biopsies, sputum cytology, repeat chest CT scans, repeat chest radiography, MRI and PET scans.

Prior to the close of the Study, each site will obtain the most recent CT Report and History and Physical (if available) for all enrolled subjects who received a benign biopsy result or a CT follow-up showing stability to re-confirm that the subjects have remained free of malignancy.

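### Protocol 8.1 and the SAP define different primary hypotheses, tests and analysis sets, and nothing says which one governs

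*Protocol*

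**What the plan says.** **Protocol, primary test.** Section 8.1 (Validation Phase) states: "The primary null hypothesis is that the relative risk of a malignant biopsy among subjects with a high risk ProLung test result to that" of low-risk subjects is 1.0. The test is a two-sided Fisher's exact test at 5%. Section 2.1 gives significance the matching meaning: "patients with a high ProLung Test result have a greater risk of developing lung cancer than patients with a low test result".

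**Protocol, analysis set.** Section 8.1 restricts the test: "The primary analysis will only include subjects who have a biopsy within 60 days of their ProLung test and have a definitive biopsy result". Subjects without a biopsy are excluded, and up to 12% are allowed for on this account and for indefinite results.

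**Protocol, elsewhere.** Other sections treat CT follow-up as an outcome.
- Section 3.0 lets the diagnosis be made "by CT follow-up detecting significant nodule growth during a 1 year time frame". It adds: "If no significant growth is detected and the nodule is not definitively diagnosed by biopsy or surgical excision, the outcome will be considered benign", unless the medical record indicates otherwise.
- Section 4.3.1 lists, as a possible reason for discontinuation, "Subject being followed by CT for nodule growth who does not receive a follow-up CT by their 1-year enrollment anniversary" or within 60 days after it. This presupposes that subjects are followed by CT.
- Section 5.10 asks sites to re-confirm freedom from malignancy in subjects "who received a benign biopsy result or a CT follow-up showing stability".
- Section 4.3.2 removes subjects from the primary analyses for "Inconclusive biopsy result", but does not list the absence of a biopsy.

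**SAP.** Sections V.A, VI and X.A make PPV and NPV co-primary. Each is tested by a one-sided exact binomial test at 0.025, and both must succeed. Section V.A.1 sets the goals at 0.638 and 0.381. Section IV.B defines the completed cases by a paired test result and either a biopsy or radiologic stability. It states no 60-day window and does not list CT growth without biopsy. Section III reads significance as showing a PPV of clinical relevance. The relative risk is not mentioned.

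**The concern.** The two documents give two definitions of a successful trial and no rule for choosing between them. The hypotheses answer different questions. One asks whether a high result carries more risk than a low result. The other asks whether each predictive value clears a fixed goal. The subjects who count also differ: the SAP admits benign subjects whom protocol 8.1 excludes.

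If the verdicts differ, the sponsor could report whichever is favourable, and a reader could not tell which was prespecified. This matters more because SAP V.A.1 already states the validation split of 111 malignant and 63 benign, while protocol 3.2 keeps the Sponsor's Statistician blind to diagnosis until recruitment and monitoring end. Any choice of primary made now is made with the diagnosis totals known.

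**Working it through.** **1. The protocol's own figure.** Section 8.1 assumes sensitivity, specificity and malignancy rate of 0.70 each.
- P(high) = 0.70 × 0.70 + 0.30 × 0.30 = 0.58.
- Risk if high = 0.49/0.58 = 0.845; risk if low = 0.21/0.42 = 0.500; RR = 1.69.
- The two-proportion sample size (two-sided 5%, 90% power, allocation 0.58 to 0.42, continuity-corrected) is 50.02 high-risk subjects, rounded up to 51. The total is 51/0.58 = 87.9, or 88.
- 88/(1 − 0.12) = 100.

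Both figures reproduce, so the protocol's sample size is sound for the protocol's own test. The defect lies elsewhere.

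**2. The two rules on one table.** PPV = TP/(TP + FP), NPV = TN/(TN + FN), RR = PPV/(1 − NPV).

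The SAP's expected cells (TP 78, FN 33, FP 22, TN 41) pass both rules. The goals need 74 of 100 positives and 37 of 74 negatives to be correct, and Fisher p is below 0.001.

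Now take TP 72, FP 25, FN 39, TN 38, with the same 111/63 split.
- PPV = 72/97 = 0.742, p = 0.019: passes.
- NPV = 38/77 = 0.494, p = 0.029: fails at 0.025, so the SAP fails.
- RR = 0.742/0.506 = 1.47. Fisher p = 0.0015 on all 174.
- Suppose 30 of the 63 benign subjects were classified by radiology and are removed in proportion, leaving 13 FP and 20 TN. Biopsy-only Fisher p = 0.015, so the protocol succeeds.

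**3. How often the verdicts differ.** Exact enumeration with TP ~ Bin(111, 78/111) and FP ~ Bin(63, 22/63). The SAP rule is applied to all 174. Fisher (p < 0.05 with RR > 1) is applied to 111 malignant and 63 − r biopsied benign subjects. Here r is the number of benign subjects classified by radiology. It is **not given in the documents**. Specificity is assumed equal in both benign groups.

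| r | Fisher power | Both goals | Protocol only | SAP only |
|---|---|---|---|---|
| 0 | 0.995 | 0.903 | 9.2% | 0% |
| 10 | 0.990 | 0.903 | 8.8% | 0.0% |
| 20 | 0.980 | 0.903 | 7.9% | 0.1% |
| 21 | 0.977 | 0.903 | 7.7% | 0.2% |
| 30 | 0.950 | 0.903 | 6.4% | 1.6% |
| 40 | 0.870 | 0.903 | 4.5% | 7.7% |
| 50 | 0.662 | 0.903 | 2.6% | 26.7% |

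The only related figure in the documents is the protocol's 12% allowance for subjects without a biopsy or definitive result: 0.12 × 174 = 20.9, about 21.

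**4. Cause of each direction.** With margins 111/63, 1,812 tables pass both rules, 878 pass Fisher only and none passes the SAP only. The largest Fisher p among SAP-passing tables is 0.002. Protocol-only success therefore comes from the tests themselves, and SAP-only success needs different analysis sets. It is possible: if 21 true negatives in the SAP's expected table were radiology cases, the biopsy-only table is 78/22/33/20 (TP/FP/FN/TN) and Fisher p = 0.056. That example requires all 21 to be true negatives, so it shows possibility, not likelihood.

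**The case against.** A reader might infer that the two tests can contradict each other equally in either direction. The documents do not support that. On common data the SAP rule is always the harder one, and the reverse disagreement depends on an unstated number of radiology cases. Inclusion criterion 4 requires every subject to be indicated for biopsy or resection, and the 12% allowance implies about 21 such cases, where SAP-only success is negligible under equal specificity. The 26.7% needs 50 of 63. Two cautions remain. The 12% is a planning figure, not a count. And if biopsied benign subjects had specificity 0.60 with the overall value unchanged (assumed), SAP-only success at 20, 30 and 40 cases would be about 2%, 7% and 18%.

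It can also be said that the protocol's hypothesis survives in the SAP: PPV + NPV > 1 is algebraically RR > 1, and SAP V.B tests it. That is true. But it is tested as a secondary endpoint, only after both co-primaries succeed, by a z-test on the SAP's set. It cannot serve as the protocol's primary analysis.

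The analysis-set conflict is partly the protocol's own. The SAP's stability rule follows protocol 3.0 and 5.10, and the biopsy-only wording of 8.1 is the outlier. This stands, and it widens what must be corrected.

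Finally, protocol 9.6 requires changes to be made by signed amendment or revised protocol but opens by speaking of study procedures, so its reach over the primary analysis is arguable. Some pages, including the front matter of both documents, were not available and could carry version information. A reader might also infer that the primary was changed after unblinding. The SAP gives diagnosis totals but no observed cross-classification with test results (its cells are simulated expectations), so the documents do not show this.

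**Conclusion.** The conflict is plain on the page and must be resolved before analysis. Two primary hypotheses, two tests and two analysis sets stand side by side, and no available section says which governs.

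On the same 174 subjects, at the SAP's expected cells, the verdicts differ about 9% of the time, always with the protocol succeeding and the SAP failing. This rests on the SAP's expected sensitivity and specificity and its fixed 111/63 split, and on no assumption about radiology cases. SAP success with protocol failure is a consequence of the differing sets alone. It is about 0.2% at 21 radiology cases, 1.6% at 30, 7.7% at 40 and 26.7% at 50, assuming equal specificity. These figures are illustrative, since they remove only benign subjects; the 60-day window or CT-growth diagnoses could remove malignant ones too.

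**What to change.** Before analysis, amend so that both documents name one primary hypothesis, one analysis set and one reference standard.

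- **If the SAP's co-primaries are kept:** revise protocol 2.1 and 8.1 (hypothesis, analysis set, sample-size basis) to match. Report RR with its 95% confidence interval and the Fisher p-value as supportive results, on completed cases and on the biopsy-only set.
- **If the relative risk is kept:** revise SAP III, V, VI and X to match. Report PPV and NPV against their goals as supportive results.
- **Either way:** make protocol 3.0, 4.3.1, 4.3.2, 5.10 and 8.1 and SAP IV.B agree on which outcomes count, including CT growth without biopsy. Give the reason for the choice, and state whether the diagnosis blind of protocol 3.2 was intact when it was made.

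The cost is an amendment to both documents, and possibly reclassification of some outcomes under the common reference standard. Two drawbacks should be acknowledged. The primary is fixed after the diagnosis totals are known, and RR on completed cases is the easier hurdle, which is why both results must be reported. If the biopsy-only set is kept, its power must be restated: by the table above it falls to 0.870 with 40 radiology cases and 0.662 with 50, so further enrolment cannot be ruled out.

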8.2 Safety/Tolerability Analyses

Subject data on AEs and SAEs will be collected during and immediately following the ProLung Test period. Treatment emergent AEs will be summarized using descriptive statistics (e.g., number and percentage of patients). Treatment emergent AEs are defined as AEs whose onset occurs, severity worsened or intensity increases after undergoing the ProLung Test. We will survey the subjects for their comfort and tolerance of the overall test procedure.

8.3 Baseline and Demographic Data

Patient information including age, gender, smoking history, occupational exposure, and ethnic background (when available) will be collected and used to summarize the baseline and demographic characteristics for each Cohort and overall.

9.0 Administrative and Ethical Requirements

9.1 Declaration of Helsinki and Ethical Review

The Study will be performed in accordance with the principles stated in the Declaration of Helsinki, FDA GCP regulations and ISO 14155: 2011 requirements. The final Study protocol, including the final version of the Informed Consent Form (ICF) to be used, must be approved by an IRB before enrollment of any patients in the Study. The opinion of the IRB will be dated and given in writing. A list of those present at the committee meeting (names and positions) should be attached. The regulatory authority and/or IRB will be informed of any SAEs and amendments to the protocol according to local and FDA requirements. All correspondence with the IRB must be filed by the Principal Investigator and a copy forwarded to the Sponsor.

9.2 Monitoring Procedures and Auditing of Data

A Study Monitor will review the Study data during, and at the end, of the investigation. All personnel involved in the Study should be prepared to make time to discuss the data with the Monitor.

The following will be reviewed by the Study Monitor:

- Subject enrollment
- Compliance with the protocol
- Informed consent verification
- Completion of the CRFs and the correction of any missing or incorrect data
- 100% Source document verification (SDV)
- Adverse event identification and reporting

- Contents of the Investigator File and Study Documents

In accordance with Good Clinical Practices (GCP), the Monitor will undertake auditing of data recorded on the CRF against the source documents. The purpose of source document verification is to verify, so far as is possible, that the information on the CRF reflects the data recorded in the patient's hospital/clinic chart. SDV will be performed with due regard for subject confidentiality and in accordance with local privacy regulations, and HIPAA requirements if any.

9.3 Subject Information and Consent

The Principal Investigator or designee will ensure that the subject is given full and adequate verbal and written information about the nature, purpose, possible risks and benefits of the Study. Subjects must also be notified that they are free to stop participating in the Study at any time without prejudice to the quality or level of care provided. Subjects will be informed that the effects of the device will be followed throughout the Study. The subject should be given the opportunity to ask questions and time to consider their participation. The Principal Investigator or designee is responsible for obtaining and documenting written informed consent from all subjects before enrollment. The subject must be given a copy of the fully executed ICF. The Principal Investigator must retain an original fully executed ICF.

9.4 Subject Data Protection

All data provided to the Sponsor will be identified by a unique subject number, thereby ensuring that the subject's identity remains unknown. The subjects should be informed in writing, that their data may be stored and analyzed in a computer, with confidentiality maintained in accordance with local regulation.

The subjects should also be informed in writing that authorized representatives of the Sponsor and/or regulatory authorities may require access to those parts of the chart records relevant to the Study, including medical history, for data verification.

The Principal Investigator is responsible for keeping a subject identification list of all subjects screened and enrolled which includes the following information: subject number, full name, and a secondary unique identifier (i.e., hospital/clinic number).

9.5 Financial Disclosure

All investigators participating in clinical studies must comply with local and national financial disclosure regulations if applicable. If required, these are to be submitted in support of an application for market approval.

The financial information typically disclosed includes four types of data. They are:

- i) significant equity interest in the Sponsor held by the Investigator equal to or exceeding US \$50,000
- ii) any financial arrangement entered into between the Sponsor and the investigator whereby the value of the compensation to the investigator for conducting the Study could be influenced by the outcome of the Study

- iii) compensation, other than that which is associated with conducting the referenced Study, paid by the sponsoring company to an investigator, exclusive of the costs of conducting the clinical Study or other sponsored clinical studies (e.g., a grant to fund ongoing research, compensation in the form of equipment or retainers for consultation or honoraria, etc.)
- iv) proprietary interest in the product tested in the covered Study held by an investigator.

To comply with this regulation, investigators are required to complete the financial disclosure form which will be supplied at site initiation. These disclosure requirements cover Principal Investigators, co-investigators and sub-investigators and their spouses and dependent children. The originals of these documents must be included in the Principal Investigator's regulatory documents.

